#### Where:

- chglnacr is the repeated measure of change in log ACR collected at Weeks 2, 4, 8, 12, 16 and 24;
- treatment takes on three levels (CSL346 8 mg/kg, CSL346 16 mg/kg and placebo)
- sglt2i\_yn is the stratification variable associated with the presence or absence of a concomitant SGLT2i at entry into the trial;
- visit is the time variable;

## 16.2 PK Parameters

Term	Definition [unit]	Calculation method
AUC day1	Partial AUC from time point 0 to time point 1 day [mass * time * volume  ]	AUC from the time of dosing to subject released from the clinic on Day 1, using the linear up/log down trapezoidal rule
AUC 0-28d	Partial AUC from time point 0 to 28 days [mass * time * volume  ]	AUC from the time of dosing to a specified 28 days, using the linear up/log down trapezoidal rule
C max	The maximum observed in serum [mass * volume  ]	
C trough	Observed concentration at the end of a dosing interval, immediately before the next dose administration [mass * volume  ]	
CL	The total body clearance of drug after IV dose or extravascular dose with known bioavailability [volume * time  ]	When the extrapolated area contributes more than 30% to the total AUC 0-∞ , data will be excluded from summary statistics unless justification is provided to support the validity of AUC 0-∞ .
T max	The time to reach maximum (peak) drug concentration in measured biological fluid [time]	

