- E:** Vital signs include BP (systolic and diastolic), body temperature, and pulse rate. Blood pressure measurements should be taken in triplicate before all other assessments. Vital signs in general will be collected before any blood samples that are collected at the same time point. At Visit 2 (Day –21), BP will be the only vital sign collected. Instructions for measuring BP will be provided in the Manual of Operations. At Visit 4 (Day 1), vital sign measurements will be taken predose, at 30, 60, and 120 minutes (± 15 minutes) after the first IV dose of IP (before the first SC dose of IP) is administered, then at 30 and 60 minutes (± 15 minutes) after SC dosing.
- F:** Height will be measured at Screening only.

- G:** Electrocardiograms must be performed in triplicate before any blood samples that are collected at the same time point.
- H:** A local assessment of echocardiogram will be performed during Screening unless an echocardiogram was performed for non-study-related reasons within 3 months before Screening.
- I:** At Visit 2 (Day -21), a blood sample will be collected for determination of serum creatinine only.
- J:** A timed 24-hour urine sample will be collected to assess eligibility (ACR) at Screening (Baseline), and to measure CSL346 levels in urine at subsequent indicated visits.
- K:** Subjects will collect urine from their first morning void on 3 consecutive days (2 consecutive days for Visit 9) leading up to and including the morning of each indicated visit.
- L:** Morning midstream urine samples will be collected to evaluate exploratory biomarkers and will also be stored for future research analyses.
- M:** Specific instructions for administration of IP are provided in the IMP Handling Manual. At Visit 4 (Day 1), an initial loading dose of IP will be administered by IV, followed at least 2 hours (but no more than 6 hours) later by the subject's normal prescribed dose by SC infusion. Subsequent doses of IP will be administered by SC infusion.
- N:** Serial blood samples for PK will be collected at Visit 4 (Day 1) predose, at 30 (\pm 5 minutes), 60 (\pm 10 minutes), and 120 (\pm 10 minutes) minutes after the first IV dose of IP (before the first SC dose of IP) is administered, then after the final vital signs measurement. Single PK samples will also be collected at all subsequent visits (before treatment on SC dosing days).

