2.2.2 Secondary Endpoints

Secondary Objective	Endpoint	Summary Measure
1	Treatment-emergent adverse events, including adverse events of special interest (AESIs) from the time of first dose of the IP through End of Study (EOS)	Number and percentage of subjects overall, by severity, by relatedness, by seriousness, and by action (ie, IP discontinuation)
2	Observed value and change from Baseline in SCr and eGFR through EOS	Mean (SD)
3	Observed value and change from Baseline in systolic and diastolic blood pressure (SBP and DBP) through EOS	Mean (SD)
4	CSL346 serum PK: 
 • Maximum concentration (C_{max}) after IV loading dose • Time to reach C_{max} in serum (T_{max}) after IV loading dose • C_{max} after first SC dose • T_{max} in serum after first SC dose • Area under the concentration-time curve in first dosing interval ($AUC_{0-\tau}$) • Trough concentration (C_{trough}) after each dose 	Mean (SD), coefficient of variation (%CV) and geometric mean for all parameters except T_{max} ; Median (minimum, maximum) for T_{max}
5	Presence of anti-drug antibody at Week 4 (Visit 7), Week 8 (Visit 8), and Week 16 (Visit 10)	Number and percentage of subjects with positive result (with reciprocal titer)

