3.1.3 Treatment Period

The Treatment Period will include 12 weeks of approximately monthly (every 4 weeks) administration of IP. Using an interactive response technology (IRT) system, eligible subjects will be randomized (1:1:2) to receive blinded IP (8 mg/kg CSL346, 16 mg/kg CSL346, or placebo).

Each subject's first dose of IP at Visit 4 (Day 1) will be an IV loading dose of 3 mg/kg CSL346 (subjects randomized to 8 mg/kg CSL346), 6 mg/kg CSL346 (subjects randomized to 16 mg/kg CSL346), or placebo (subjects randomized to placebo). All IV loading doses will be in a total volume of 10 mL and infused over the course of approximately 20 minutes. The subject will then be monitored for approximately 2 hours, during which AEs and vital signs will be recorded periodically as described in the [Schedule of Assessments](#) and [Section 8.1.1](#). If no clinically relevant AEs are observed during this time, the subject's first SC dose of IP will be administered as an 8 mg/kg CSL346, 16 mg/kg CSL346, or placebo 20 mL SC infusion over the course of approximately 40 minutes.

Subjects will receive 3 subsequent SC infusions at Visit 7 (Week 4), Visit 8 (Week 8), and Visit 9 (Week 12) for a total of 4 SC doses.

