3.2 Dose and Dosing Regimen

At Visit 4 (Day 1), CSL346 will be administered at an initial loading dose of 3 mg/kg or 6 mg/kg IV, followed by 8 mg/kg or 16 mg/kg SC, respectively, at least 2 hours but no more than 6 hours later. Subsequent SC infusions (8 mg/kg or 16 mg/kg per dose) will be administered every 4 weeks for 12 weeks.

Subjects experiencing a mild injection site reaction deemed unacceptable by the subject or Investigator may have administration and / or dose adjustments (see [Section 5.1.3.1](#)).

The IDMC will evaluate the need for dose de-escalation during planned reviews of emerging data (see [Section 3.6.1](#)) and may discontinue the 16 mg/kg CSL346 dose level as per predefined dose level stopping criteria ([Section 3.7.2](#)).

Placebo consists of normal saline for IV and SC infusion. Dosing administration, regimen, and volume will be matched to CSL346.

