Details related to the collection, preparation, and transfer of blood and urine samples for laboratory assessments will be provided in the laboratory manual. Tests resulting in abnormal central laboratory values during the study period that have been classified by the Investigator as clinically significant should be repeated by the central laboratory as soon as possible after receiving the laboratory report to rule out laboratory error.

Refer to [Section 9.6.2](#) for assessment of other abnormal laboratory values.

Vital Signs

Vital signs include BP (systolic and diastolic), body temperature, and pulse rate. Blood pressure measurements should be taken in triplicate before all other assessments. Vital signs in general will be collected before any blood samples that are collected at the same time point. At Visit 2 (Day -21), BP will be the only vital sign collected.

Subjects must be seated for at least 5 minutes before vital sign measurements are taken. Instructions for measuring BP will be provided in the Manual of Operations. At Visit 4 (Day 1), measurements will be taken predose, 30, 60, and 120 minutes after the first IV dose of IP but before the first SC dose of IP is administered, then 30 and 60 minutes after SC dosing. Additional measurements will be taken at Visit 2, at Visit 5 (Day 8, approximate T_{max}), at Visit 6, before each subsequent SC IP administration (at Visits 7, 8, and 9), and during Follow-up (at Visit 10 and EOS). Analysis will be based on the mean of 3 measurements at each timepoint.

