### **12.3 Pharmacokinetic Statistical Analyses**

Dose-adjusted PK parameters of  $AUC_{\text{day1}}$ ,  $AUC_{0-28d}$ ,  $C_{\text{max}}$  after IV loading dose, and  $C_{\text{max}}$  after first SC dose will be natural log transformed and analyzed in an analysis of variance model, comparing the 8 mg/kg and 16 mg/kg dose levels. The model will be based on the dose level as the only effect. The estimate and 90% CI for the difference of 16 mg/kg – 8 mg/kg will be exponentiated to obtain the point estimate and CI for the geometric mean ratio. Dose proportionality is supported when the 90% CI includes the 1.

Graphical displays of CSL346 will include a separate display for each natural log transformed PK parameter versus natural log transformed dose to evaluate dose proportionality.

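### As the SAP defines them, Cmax and Tmax after the first SC dose would in most subjects record the IV loading dose, and Tmax would mix values of hours with values near 7 days

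*SAP*

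**What the plan says.** Protocol 2.2.2 lists Cmax after the first SC dose and Tmax "in serum after first SC dose" among the PK measures for secondary objective 4.

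**Dosing.** On Day 1, Protocol 3.2 starts active subjects on "an initial loading dose of 3 mg/kg or 6 mg/kg IV". The timing of the first SC dose relative to that load is given by the phrase "followed by 8 mg/kg or 16 mg/kg SC, respectively, at least 2 hours but no more than 6 hours later". Protocol 3.1.3 points to the short end of that range: "The subject will then be monitored for approximately 2 hours", after which the SC infusion runs for about 40 minutes.

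**Sampling.** Note N to the Schedule of Assessments places Day 1 samples before dosing and at 30, 60 and 120 minutes after the IV dose, "then after the final vital signs measurement. Single PK samples will also be collected at all subsequent visits". Note E puts the last Day 1 vital signs at 60 minutes after SC dosing. The samples in the first SC interval are therefore one on Day 1, then Day 8, Day 15 and Day 29 before dosing.

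**Expected peak.** Protocol 8.1.1 marks Day 8 as roughly the time of the peak: "Additional measurements will be taken at Visit 2, at Visit 5 (Day 8, approximate", where the term that follows is Tmax.

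**Derivation.** SAP 16.2 defines Cmax as "The maximum observed in serum", with an empty calculation cell, and Tmax as the time to the peak. SAP 8.2.1 starts the PK clock at the IV loading dose. SAP 12.2 summarises both SC parameters. SAP 12.3 states that Cmax "after first SC dose will be natural log transformed and analyzed in an analysis of variance model"; the model contrasts the two dose levels.

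**The concern.** The label says SC, but the rule takes the largest concentration seen after the SC dose, whatever its source. The first eligible sample comes when the IV load is still near its peak and SC absorption has barely started. If that sample is the largest, the reported SC Cmax is in substance an IV concentration and the reported SC Tmax is a matter of hours, although the protocol expects a peak near Day 8.

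Two listed secondary PK endpoints are at stake, as is the meaning of one of the dose-proportionality comparisons. SC is the maintenance route, so a reader of the report would take these figures as evidence on SC absorption.

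**Working it through.** **1. Reproduce Table 2.** 472/74 = 6.38 (stated 6.3), 472/149 = 3.17 (3.2), 5839/1336 = 4.37 (4.4) and 5839/2720 = 2.15 (2.1). The inputs agree with the plan to rounding.

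**2. Quantities from the documents.**
- CL = 20,000/5839 = 3.43 mL/day/kg.
- Central volume Vc = 20,000/472 = 42.4 mL/kg.
- SC bioavailability F = 0.61 (Protocol 1.2.3); half-life about 30 days (Protocol 3.3.2).
- Check: F × dose/CL = 0.61 × 8000/3.43 ≈ 1425 µg·day/mL against the stated 1336. This is 6.6% high and inside 970 to 1921.

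**3. IV peak.** PK is stated to be dose proportional, so 472 × 3/20 = 70.8 µg/mL and 472 × 6/20 = 141.6 µg/mL. These are close to the predicted regimen Cmax of 74 and 149.

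**4. Time of the Day 1 post-SC sample.** On the IV clock, 20 min + 2 h + 40 min + 60 min = 4 h; with a 6 h gap it is 8 h. From the start of the SC infusion it is about 1.7 h.

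**5. One worked case, low arm.** Assume a two-compartment model with terminal half-life 30 days, distribution half-life 2 days, SC-alone Tmax 7 days (which solves to an absorption rate of 0.126/day) and a 2 h gap.
- α = ln2/2 = 0.3466 and β = ln2/30 = 0.0231 per day. k10 = CL/Vc = 0.0808. k21 = αβ/k10 = 0.0991.
- IV weights: (α − k21)/(α − β) = 0.765 and (k21 − β)/(α − β) = 0.235.
- IV part at 4 h: 70.8 × (0.765 × 0.944 + 0.235 × 0.996) = 67.7.
- SC part at about 1.7 h: (0.61 × 8000/42.4) × (1 − e^(−0.126 × 1.67/24)) = 115 × 0.0087 = 1.0.
- Total 68.7 µg/mL, of which 67.7/68.7 = 99% is IV drug.
- IV part at Day 8: 70.8 × (0.765 × 0.088 + 0.235 × 0.851) = 18.9. The model total is 49.7, so the IV share is 38%.
- Day 15 and Day 29 totals: 39.0 and 26.6 µg/mL.

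Here the Day 1 post-SC sample is the highest of the four.

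**6. Range.** The documents give neither a distribution rate nor an absorption rate, so both were varied (intercompartmental clearance 1.5 to 120 mL/day/kg; absorption rate 0.12 to 1.0 per day; terminal half-life 20 to 33 days; CL 3.43 or 3.65). A set was kept if regimen Cmax was below 78, SC Tmax was 4 to 10 days, and the 16 mg/kg level at Week 24 was 15.5 ± 2 µg/mL. The last condition follows from the protocol's 59% of subjects above 14.4. Low-arm results for the 250 sets kept:

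| | 2 h gap | 6 h gap |
|---|---|---|
| Day 1 post-SC sample, µg/mL | 49–70 | 36–68 |
| Sets in which it is the highest | 97% | 70% |

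IV drug is about 87 to 99% of that sample. Day 8 is 41 to 66 µg/mL. The IV share at Day 8 is 31 to 38% with SC Tmax of 4 to 7 days, and up to 42% with slower absorption.

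**7. Between-subject variability.** Assumed log-SDs were 0.17 on CL (from the 970 to 1921 interval, read as a 95% between-subject range), 0.2 on Vc, 0.17 to 0.3 on the other rates and volumes and half of that on F, with 10% residual error. The Day 1 post-SC sample is the maximum in 77 to 79% of subjects with a gap of 2 to 2.5 h, 68 to 71% with 2 to 6 h, and about 61% with 5.5 to 6 h. The median IV share of the recorded Cmax is about 96%.

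**8. High arm.** Both doses double, so concentrations double and the shares stay the same.

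**The case against.** **The ranking rests on assumed rates.** This stands. A reader might infer from the dose-scaled IV peak that the Day 1 post-SC sample is the maximum in every subject. The documents do not support that. With terminal half-life 30 days, distribution half-life 6 h, SC Tmax 6.2 days and a 6 h gap, Day 1 is 42.7 and Day 8 is 44.8 µg/mL, with a regimen peak of 69.8, still compatible with Table 2. With 25 days, 4 h and a 2 h gap, the values are 50.3 and 52.2. Fast distribution moves the maximum to Day 8.

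**The derivation rule may sit elsewhere.** SAP 12 sends non-compartmental work to the sponsor's guideline PK-GDL-01, which is not available here, and allows concentrations to be excluded and flagged. That guideline may contain a window rule. The fair statement is that the SAP gives none, and a rule that decides two named endpoints belongs there.

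**The dose comparison is not distorted.** This also stands. A reader might infer a biased dose-proportionality result. Because IV and SC doses double together, the 16 versus 8 mg/kg ratio is not biased; it simply tests mainly the IV dose.

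**The impact is limited.** Also correct. These are PK summaries in a phase 2a study, AUC over 28 days and trough levels are reported as well, and population PK is already planned.

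**Conclusion.** The point holds, with moderate confidence. Followed as written, the SAP would report a Cmax after the first SC dose that mostly repeats IV exposure. The Day 1 post-SC sample would be the recorded maximum in roughly 60 to 80% of subjects and Day 8 in most of the rest, more often so with a distribution half-life of about 4 to 8 h or less, or a gap near 6 h.

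Tmax would be a mixture: about 4 to 8 h on the SAP's IV-dose clock (about 2 h from the start of the SC infusion) in one group, and about 7 days in the other. A median of that mixture describes neither route. Because SAP 8.2.1 names only the IV clock, the hours figure itself depends on a time zero that is not stated for the SC parameters.

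The proportions rest on the assumed distribution and absorption rates and the assumed variability. The timing facts, the IV peak of about 71 µg/mL and the missing window come from the documents. The primary ACR analysis is not touched.

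**What to change.** In SAP 12.2, 12.3 and 16.2:

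- Derive Cmax and Tmax for the first SC interval from the Day 8, Day 15 and Day 29 predose samples only.
- State time zero for them as the start of the SC infusion.
- Label both as following IV load plus first SC dose, because about 31 to 38% of the Day 8 level (up to 42% with slow absorption) is still IV drug.
- Restrict Cmax and Tmax after the IV loading dose to samples taken before the SC dose.
- Take SC-only peak and time from the population PK analysis already planned.

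Write this as a parameter-specific window rather than an exclusion flag. SAP 12.1 drops concentrations excluded from parameter derivation from the summary statistics and mean plots, and the Day 1 post-SC value should stay there and in the AUCs.

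The cost is SAP wording, with no new samples. The downside is that three sparse time points make Tmax coarse, close to restating the visit day, and Cmax slightly low.

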### 16.3 Standard of Care Therapies

Drug Class	ATC Code (ATC 2)
Antihypertensive drugs	C02
Diuretic drugs	C03
Peripheral vasodilators	C04
Beta blocking agents	C07
Calcium channel blockers	C08
Agents acting on the renin-angiotensin system	C09

### 16.4 Sodium-Glucose Co-Transporter 2 (SGLT2) Inhibitors

Drug Class	ATC Code (ATC 4)
Sodium-glucose co-transporter 2 (SGLT2) inhibitors	A10BK

### 16.5 SMQs for COVID-19 associated AEs

SMQ	Code	Level
Asymptomatic COVID-19	10084459	PT
Coronavirus infection	10051905	PT
Coronavirus test positive	10070255	PT
COVID-19	10084268	PT
COVID-19 immunisation	10084457	PT

SMQ	Code	Level
COVID-19 pneumonia	10084380	PT
COVID-19 prophylaxis	10084458	PT
COVID-19 treatment	10084460	PT
Exposure to SARS-CoV-2	10084456	PT
Multisystem inflammatory syndrome in children	10084767	PT
Occupational exposure to SARS-CoV-2	10084394	PT
SARS-CoV-2 antibody test positive	10084491	PT
SARS-CoV-2 carrier	10084461	PT
SARS-CoV-2 sepsis	10084639	PT
SARS-CoV-2 test false negative	10084480	PT
SARS-CoV-2 test positive	10084271	PT
SARS-CoV-2 viraemia	10084640	PT
Suspected COVID-19	10084451	PT

## 16.6 COVID-19 Vaccines

Drug Class	ATC Code
COVID-19 vaccines	J07BX03

## 16.7 Factors to be Addressed in Per Protocol Analysis Set

The following define major events which could result in subjects' data being removed from the per protocol analysis set. Subjects' data may be removed completely or from the time of the major event up to the end of subject's study participation.

At a specific time point, ACR measurements are to be used in summaries and analysis as long as there are at least 2 FMVs for that time point (4 FMVs for baseline) available.

- Extrinsic factors with the potential to impact ACR during treatment period. For any such occurrences, data points at or beyond the date of the occurrence will be excluded from analysis. [These data will be provided by CSL.]
  - Protocol deviations:
    - Subjects with substantial change in blood pressure medications or DKD medications;
    - Prohibited concomitant medications;
    - Initiation of lipid lowering agent;
    - Change in SGLT2i doses;
    - Change in dose in agents that impact tubular secretion of serum creatinine (fibrates).
    - Missed intermittent dose
  - Cardiac AESI with heart failure.
- Study drug [to be derived by Parexel]:
  - For subjects receiving fewer than 4 doses of the investigational product, all data on or after the date of the last dose + 4 weeks + 1 day will be excluded. If no dose is administered then all data for that subject will be excluded.
- Violation of study entry criteria. In these cases, all data from these subjects will be excluded from analysis. [These data will be provided by CSL.]
  - Baseline Glycosylated HbA1c  $\geq 12\%$ ;
  - Change in SCr from Visit 1 (<63 Days before Day 1) to Visit 2 (Day -21)  $> 0.3$  mg/dL (26.5  $\mu\text{mol/L}$ );
  - Uncontrolled hypertension: SBP  $> 160$  mmHg or DBP  $> 100$  mmHg prestudy (SBP $>150$  mmHg at randomization).

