### 8.4 Study Periods Relative to Treatment

All data will be assigned to one of the four study time periods defined below.

**Screening** is defined as the time from signing of the informed consent form through Visit 2.

The **Lead-in Period** is defined as the time Post-Visit 2 (from SC saline test infusion) up to subject randomization.

The **Treatment Period** is defined as the time from randomization through Visit 9 (12 weeks after the first administration of IP).

**Follow-up** begins after the last administration of IP at Visit 9 through the EOS visit 12 weeks later.

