### 10.1.2 Primary Efficacy Analysis

The primary analysis is a mixed effects model, repeated measures (MMRM) analysis of the change from baseline through 24 weeks of log ACR, with the primary treatment comparison at Week 16 (Visit 10). The model will include treatment (at 3 levels: 8 mg/kg CSL346, 16 mg/kg CSL346, and placebo), baseline log ACR, the stratification variable related to the concomitant use of SGLT2i, visit (as a categorical factor), and interactions between visit and each of the other model terms as factors. The primary comparison of interest will be calculated using a contrast of  $0.5 (8 \text{ mg/kg CSL346} + 16 \text{ mg/kg CSL346}) - \text{Placebo}$ . Please see [Section 16.1](#) for the corresponding SAS Code for the MMRM model. Because this is an early development study and the first study in subjects with T2DM, the one-sided alpha level to be employed for this test is 0.10. Estimated treatment effect of individual CSL346 dose levels versus placebo will also be summarized. The treatment comparisons will be expressed as a percent difference in treatments, calculated as  $100\% \times (\text{geometric mean ratio of the treatment comparison} - 1)$ . The covariance matrix structure to be employed in the primary analysis will be an unstructured pattern. In the event of model convergence issue, a Toeplitz heterogeneous structure will be employed. If the model still fails to converge an autoregressive structure ARH(1) will be assumed.

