### 10.1.3 Sensitivity Analyses of Primary Endpoint(s)

A sensitivity analysis will be conducted with regard to the primary endpoint. The analysis will be identical to the one identified above, except that the Per Protocol Analysis Set is used. In this analysis, subjects will be assigned to the treatment actually received. In the event of a decrease in dose (from 16 mg/kg to 8 mg/kg) the subject will be assigned to the highest dose treatment received. This analysis will exclude data following major protocol deviations and other factors which may influence the primary outcome. Major protocol deviations will be determined without knowledge of treatment assignment (i.e., prior to unblinding). [Appendix 16.7](#) provides a list of major protocol deviations and other reasons for exclusion from the Per Protocol Analysis Set.

The second (to be conducted for Per Protocol Analysis Set) sensitivity analysis is a tipping point analysis that will employ multiple imputation for missing data (missing change from baseline in ACR) using multiple regression to provide multiple complete data sets [[Buuren 2018](#)]. The same MMRM model will be used to analyze the imputed complete data sets (missing ACR values will be imputed for planned ACR assessments up to the individual subjects last performed visit before EOS and EOS visit). If the original analysis indicates a significant effect, the tipping point analysis adds a value, delta, to the imputation model to assess the sensitivity of the “missing at random” assumption. In this case, the delta is

increased (decreased) until statistical significance is lost. A conclusion of the sensitivity analysis is based on whether the value of delta at the time significance is lost is interpreted as likely given the data observed.

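### SAP 16.7 as written ends the Per-Protocol exclusions for ACR-altering events at Week 12, while SAP 6.4 and 10.1.3 set no time limit and the primary comparison is at Week 16

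*SAP*

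**What the plan says.** SAP 10.1.3 gives the purpose of the Per-Protocol sensitivity analysis: "This analysis will exclude data following major protocol deviations and other factors which may influence the primary outcome". SAP 6.4 describes the set in similar terms, as leaving out data that follow events able to affect ACR. Neither section limits when the event must occur, and both send the reader to 16.7 for the criteria.

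SAP 16.7 opens its main bullet with "Extrinsic factors with the potential to impact ACR during treatment period". The listed factors are:
- a substantial change in blood pressure or DKD medication
- a prohibited medication
- the start of a lipid-lowering agent
- a change in SGLT2 inhibitor dose
- a change in fibrate dose
- a missed intermittent dose
- a cardiac AESI with heart failure

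The consequence is stated as "For any such occurrences, data points at or beyond the date of the occurrence will be excluded from analysis". The section's introduction adds: "Subjects' data may be removed completely or from the time of the major event up to the end of subject's study participation".

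SAP 8.4 sets out the periods and says: "All data will be assigned to one of the four study time periods defined below". Its entry for treatment "is defined as the time from randomization through Visit 9 (12 weeks after the first administration of IP"), which closes that period at the Week 12 visit. Whatever comes later, up to EOS, counts as Follow-up. The schedule in SAP 16.8 also places Week 16 under Follow-up. The primary model in SAP 10.1.2 is fitted "with the primary treatment comparison at Week 16 (Visit 10").

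**The concern.** The Per-Protocol analysis is the planned look at the Week 16 effect with outside influences on ACR taken out. The primary estimand (SAP 10.1.1) follows a treatment policy strategy and deliberately ignores such influences, so this job falls to the Per-Protocol set. Under the literal criteria, an SGLT2 inhibitor dose change at Week 3 removes a subject's later data, but the same change at Week 13, shortly before the endpoint, does not meet the stated trigger.

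Three planned outputs depend on the set: the Per-Protocol MMRM, the tipping-point analysis (SAP 10.1.3), and the additional KIM-1, NGAL, EGF and MCP-1 analyses (SAP 10.3). If late medication changes differ between arms, the Per-Protocol contrast at Week 16 would keep an influence that it was meant to remove. A difference is conceivable, because raised blood pressure is a listed potential risk (Protocol 1.4) and blood pressure AESIs are managed according to standard of care (Protocol 9.1.3.4).

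**Working it through.** **1. Which window applies.** Three readings of 16.7 were tried against 8.4.
- The treatment-period limit applies to when the event occurs. The trigger then ends at Visit 9, Day 85.
- The limit applies to when ACR is affected. Week 16 ACR is still outside the Treatment Period, so the gap remains.
- The introductory sentence of 16.7, which runs to the end of participation, widens the trigger. It does not: it says how long data are removed once an event qualifies, not when the event must occur.

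**2. Length of the gap** (study days and windows from the schedule: Visit 9 is Day 85 ± 5, Visit 10 is Day 113 ± 7).
- Nominal: 113 − 85 = 28 days (Days 86 to 113). From Day 1 to Day 113 is 112 days, and 28/112 = 25%.
- Shortest: (113 − 7) − (85 + 5) = 16 days.
- Longest: (113 + 7) − (85 − 5) = 40 days.

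**3. How other rules treat the same interval.** In 16.7, the rule for subjects with fewer than four doses keeps data until four weeks and a day after the last dose, and the entry-criteria rule has no time limit. The COVID-19 supplemental analysis (SAP 10.1.2) acts on a positive test at any time during the study. Protocol 5.3.1 asks for the stable background regimens to stay unchanged for the whole of participation. A missed intermittent dose can only occur within the Treatment Period, so the limit does no harm to that item.

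**4. The plan's own figures, as a yardstick** (SAP 4.4: SD 0.65, 94 completers, 27% reduction, one-sided alpha 0.10).
- ln(0.73) = −0.315.
- Standard error = 0.65 × √(2/47) = 0.134.
- Smallest significant difference, t on 92 df: 1.291 × 0.134 = 0.173, as stated.
- Power: 85.4% (noncentral t) or 85.7% (normal approximation), against 85% stated.

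The sample size reproduces and is not in question.

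**5. Possible size, on assumed rates.** The documents give no rate of late medication changes. Let Δp be the between-arm difference in the share of subjects with a late change, and r the proportional fall in ACR each change causes. The shift in the Week 16 contrast is Δp × ln(1 − r).
- Low end, Δp = 2 points, r = 20%: 0.02 × ln(0.80) = −0.0045.
- Middle, Δp = 5 points, r = 30%: 0.05 × ln(0.70) = −0.018.
- High end, Δp = 10 points, r = 50%: 0.10 × ln(0.50) = −0.069.

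Against the 0.173 threshold these are about 3%, 10% and 40%. The sign depends on the arm: ACR-lowering changes in placebo dilute the contrast, and in CSL346 they inflate it.

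**6. Cost of closing the gap, on assumed rates.** If 2%, 5% or 10% of the 94 Week 16 values were newly excluded, 92.1, 89.3 or 84.6 would remain. Power for the planned effect would be about 85.1%, 84.3% or 82.8% (normal approximation, from 85.7%).

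**The case against.** A reader might infer that late events definitely stay in the Per-Protocol analysis. The documents do not go that far. The body of the SAP (6.4 and 10.1.3) has no time limit, and a Week 13 SGLT2 inhibitor change fits both descriptions. The limiting words in 16.7 are uncapitalised and do not refer to 8.4. The section is also permissive: listed events could lead to removal, the sponsor supplies the occurrences, and SAP 9.2 leaves the final assignment to a blinded data review meeting. The four-weeks-after-last-dose rule in the same section suggests that the authors may have regarded the month after the final dose as treated time. All of this stands, and it makes the outcome for late events undetermined rather than fixed. It does not supply a rule: 6.4 and 10.1.3 both defer to 16.7, and 8.4 assigns all data to its defined periods.

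A reader might also infer a bias of known size against or in favour of CSL346. Without event rates that is unsupported. A scenario with changes in one arm only and none in the other is an illustration, and the requirement to keep background regimens unchanged argues against high rates.

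Lastly, exclusion is not free of bias. Dropping data after post-randomization events that may respond to blood pressure or ACR can itself introduce selection. That is a general limit of the Per-Protocol analysis. It does not justify treating Week 3 and Week 13 events differently.

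**Conclusion.** The point holds as an unreconciled inconsistency: the operative appendix is narrower than the stated purpose of the analysis. Its firm size is the uncovered interval: 28 days nominally, 16 to 40 with visit windows, immediately before the primary endpoint. This rests on reading the treatment period in 16.7 as the one defined in 8.4. Any effect on the estimate is unknown in size and direction; the 0.004 to 0.07 log-unit range in the working depends wholly on assumed rates.

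Only the extrinsic-factor bullet is concerned. A reader might take this as a flaw in the main result, but the primary ITT treatment-policy analysis and the sample size are untouched. The consequence is confined to the Per-Protocol sensitivity analysis, the tipping-point analysis and the added Per-Protocol biomarker analyses. It should be corrected because the written rule would otherwise leave a judgement call on data next to the endpoint.

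**What to change.** Before the interim unblinding, change the extrinsic-factor bullet in SAP 16.7 so that the limit to the treatment period becomes *from randomization through the last ACR assessment (EOS)*. Keep the existing rule that data on or after the event date are excluded. An event between Visit 9 and Visit 10 then removes Weeks 16 and 24, and an event after Visit 10 removes only Week 24. Align 6.4 and 10.1.3 with the same window. SAP 8.4 can stay as it is, since the adverse event tables in 11.2 also use its periods.

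Timing matters because SAP 6.4 plans a second data review meeting before final lock, which comes after the interim unblinding. A written rule removes the need for discretion at that stage.

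The cost is one phrase and two alignments. Concomitant medications and adverse events are already collected through the last visit, so no new data are needed. A few more Week 16 values will leave the Per-Protocol set, with the small loss of power shown above, and the report should carry the usual caveat about selection from excluding data after post-randomization events.
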